8.2. Eligibility Assessment (Screening) Failures

A subject who has at least one study procedure performed (in addition to signing a consent form) and is assigned a Subject ID, but is not randomized, is classified as having failed study entry and deemed a Screen Failure. Subject ID, demography and reason for screen failure will be recorded in the electronic CRF.

9. ADVERSE EVENT DEFINITIONS

The Investigator is responsible for the detection and documentation of events meeting the criteria and definition of an adverse event (AE) or serious adverse event (SAE), as provided in this protocol. During the study when there is a safety evaluation, the Investigator or site staff will be responsible for detecting, documenting and reporting AEs and SAEs as detailed in this section of the protocol. Country specific safety reporting requirements are detailed further in the Safety Management Plan for the protocol.

9.1. Definition of an AE

An AE is any untoward medical occurrence in a subject or clinical investigation subject administered a pharmaceutical product and that does not necessarily have a causal relationship with this treatment. An AE can therefore be any unfavorable and unintended sign (including an abnormal laboratory finding), symptom, or disease temporally associated with the use of an investigational product whether or not related to the investigational product.

AEs will be recorded from the time of first application of the investigational product and until the final visit.

9.1.1. Treatment Emergent Adverse Event (TEAE)

Treatment emergent AEs (TEAEs), those that occur after the first dose of study medication, are undesirable events not present prior to investigational product treatment, or an already present event that worsens either in intensity or frequency following treatment.

9.2. Definition of a SAE

An SAE (experience) or reaction is any untoward medical occurrence that at any dose:

- a. Results in death.
- b. Is life-threatening and/or sight threatening.

NOTE: The term "life-threatening" or "sight threatening" in the definition of "serious" refers to an event in which the subject was at risk of death or loss of vision at the time of the event; it does not refer to an event which hypothetically might have caused death or loss of vision if it were more severe.

- c. Requires in subject hospitalization or prolongation of existing hospitalization.

NOTE: In general, hospitalization signifies that the subject has been detained (usually involving at least an overnight stay) at the hospital or emergency ward for observation and/or treatment that would not have been appropriate in the physician's office or outpatient setting. Complications that occur during hospitalization are AEs. If a complication prolongs hospitalization or fulfills any other serious criteria, the event is serious. When in doubt as to whether "hospitalization" occurred or was necessary, the AE should be considered serious.

- d. Results in persistent or significant disability/incapacity.

NOTE: The term disability means a substantial disruption of a person's ability to conduct normal life functions. This definition is not intended to include experiences of relatively minor medical significance such as uncomplicated headache, nausea, vomiting, diarrhea, influenza and accidental trauma, which may interfere or prevent everyday life functions but do not constitute a substantial disruption.

- e. Is a congenital anomaly/birth defect.

Medical or scientific judgment should be exercised in deciding whether reporting is appropriate in other situations, such as important medical events, that may not be immediately life threatening or result in death or hospitalization but may jeopardize the subject or may require medical or surgical intervention to prevent one of the other outcomes listed in the above definition. These should also be considered serious. Examples of such events are invasive or malignant cancers, intensive treatment in an emergency room or at home for allergic bronchospasm, blood dyscrasias or convulsions that do not result in hospitalizations, or the development of drug dependency or drug abuse.

9.2.1. Clinical Laboratory Abnormalities and Other Abnormal Assessments as AEs and SAEs

Clinically significant abnormal laboratory findings or other abnormal assessments that are present at baseline and significantly worsen following the start of the study will be reported as AEs and SAEs.

The Investigator will exercise his/her medical and scientific judgment in deciding whether an abnormal laboratory finding or other abnormal assessment is clinically significant.

9.3. Assigning Causality

The Principal Investigator or medically qualified Sub-investigator, listed on the FDA Form 1572, must make a determination of the relationship of the AE or SAE to the investigational product using the following categories:

Definitely related: This category applies to those AEs that the Investigator feels are incontrovertibly related to the IP. An AE may be assigned an attribution of definitely related if or when it meets all of the following criteria: (1) it follows a reasonable temporal sequence from administration of the IP; (2) it could not be reasonably explained by the known characteristics of the subject's clinical state, environmental or toxic factors, or other modes of therapy administered to the subject; and (3) it follows a known response pattern to treatment with IP.

Probably related: This category applies to those AEs which, after careful medical consideration at the time they are evaluated, are felt with a high degree of certainty to be related to the IP. An adverse event may be considered probable if or when (must meet at least three of the four criteria): (1) it follows a reasonable temporal sequence from application of the IP; (2) it could not readily have been produced by subject's clinical state, environmental or toxic factors, or other therapies administered to the subject; (3) it disappears or ameliorates upon discontinuation of the IP; or (4) it follows a known response pattern to treatment with IP.

Possibly related: This category applies to those AEs which, after evaluation are judged unlikely to be related to the IP, but this cannot be ruled out with certainty. An adverse event may be considered possible if or when (must meet at least two of the four criteria): (1) it follows a reasonable temporal sequence from application of IP; (2) it could not readily have been produced by subject's clinical state, environmental or toxic factors, or other therapies administered to the subject; (3) disappears or is decreased upon discontinuation of the IP; or (4) it follows a known response pattern to treatment with IP.

Unlikely to be related: In general, this category can be considered applicable to those adverse events which, after careful medical consideration at the time they are evaluated, are judged likely to be unrelated to the IP. An adverse event may be considered unlikely if or when (must meet at least two of the four criteria): (1) it does not follow a reasonable temporal sequence from application of IP; (2) it could not readily have been produced by subject's clinical state, environmental or toxic factors, or other therapies administered to the subject; (3) disappears or is decreased upon removal of the IP; or (4) it does not follow a known response pattern to treatment with IP.

Unrelated: This category applies to those adverse events which, after careful consideration at the time they are evaluated, are clearly and incontrovertibly due to extraneous causes (disease, environment, etc.) and determined with certainty to have no relationship to the study IP.

This causality assessment must be signed and dated by the person making the evaluation in source documents.

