7.8. Unmasking

The Investigator may unmask a subject's treatment assignment only in the case of an emergency when knowledge of the investigational product is essential for the clinical management or welfare of the subject. [REDACTED]

[REDACTED]

[REDACTED]

If a drug-related serious adverse event (SAE; as defined in [Section 9.2: "Definition of an SAE"](#)) is reported, the Medical Monitor may unmask the treatment assignment for the individual subject. If an expedited regulatory report to one or more regulatory agencies is required, the report will identify the subject's treatment assignment. When applicable, a copy of the regulatory report may be sent to the Investigator in accordance with relevant regulations, Sponsor policy or both.

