The relationship of each AE or SAE to the study drug should be determined by the Investigator using these explanations: definitely related, probably related, possibly related, unlikely to be related, and unrelated. Only definitely, probably, and possibly related TEAEs will be considered as treatment-related TEAEs. For TEAEs prior to rescue medication use, only those TEAEs with an onset date prior to the date that rescue medications were first used will be included.

Clinically significant abnormal laboratory findings or other abnormal assessments that are present at baseline and significantly worsen following the start of the study will be reported as AEs and SAEs. The Investigator will exercise his/her medical and scientific judgment in deciding whether an abnormal laboratory finding or other abnormal assessment is clinically significant.

Verbatim descriptions of AEs will be mapped to MedDRA [REDACTED] terms and presented in a data listing. Adverse events recorded in the eCRF which began prior to treatment will not be included in the summary tables but will be included in the AE data listings. All AEs, SAEs, and TEAEs will be presented separately in subject data listings. The TEAEs leading to study treatment discontinuation will also be listed separately.

An overall summary will be presented that includes the number of events and the number and percentage of subjects who experienced at least one TEAE, by treatment group and over all subjects. This summary will also include breakdowns of TEAEs further categorized as ocular (study eye and, for subjects with bilateral injury, fellow eye separately) or non-ocular, treatment-related TEAEs, TE-SAEs, TEAEs leading to treatment withdrawal, TEAEs leading to death, TEAEs by maximal severity, and TEAEs by relationship to study drug.

Treatment-emergent adverse events (TEAEs), those that occur after the first dose of study medication, will be summarized by treatment group using frequency and percentages for each SOC and PT within each SOC. Similar summaries will be presented for treatment related TEAEs, TEAEs by maximum severity, serious TEAEs, and TEAEs leading to test article discontinuation.

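### Protocol 9.3 defines Possibly related and Unlikely to be related so that they overlap, and SAP 15.1 places its treatment-related cut between them

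*Protocol*

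**What the plan says.** Protocol 9.3 gives five causality categories. Each opens with a descriptive sentence, and all but the lowest add numbered criteria.

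- Probably related: events that "are felt with a high degree of certainty to be related to the IP"; at least three of four criteria.
- Possibly related: events "judged unlikely to be related to the IP, but this cannot be ruled out with certainty". The rule is "An adverse event may be considered possible if or when (must meet at least two of the four criteria".
- Unlikely to be related: events that "are judged likely to be unrelated to the IP". The rule is "An adverse event may be considered unlikely if or when (must meet at least two of the four criteria".
- Unrelated: requires certainty that there is no relationship; no numbered criteria.

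SAP 15.1 draws the analysis line: "Only definitely, probably, and possibly related TEAEs will be considered as treatment-related TEAEs". That line feeds the overall TEAE summary, Table 14.3.7 (SAP section 20) and Listing 16.2.7.2.3 (SAP section 22). SAP 15.1 also plans summaries by strongest relationship to study drug.

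**The concern.** The SAP's cut falls between two categories whose opening sentences express one judgement. An investigator who thinks the product probably did not cause an event, but cannot exclude it, can support either label from the text. One label enters the treatment-related tables and the other does not.

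The opening sentences also drop from near-certainty under Probably related straight to an unlikely relation under Possibly related. The middle judgement, a reasonable but uncertain relation, is described nowhere in them.

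What is at stake is whether the treatment-related counts can be reproduced across raters and sites. Depending on the wording a rater follows, a doubtful event is counted or left out, so the count can move in either direction.

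**Working it through.** The documents state no figure on this point, so there is none to reproduce. The check has two parts.

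**1. Opening sentences side by side**

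| Investigator's judgement | Opening sentence that fits |
|---|---|
| Certain there is no relation | Unrelated |
| Relation unlikely but not excluded | Possibly related and Unlikely to be related |
| Reasonable but uncertain relation | none |
| High degree of certainty of a relation | Probably related (or Definitely related) |

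The qualifier about not being able to rule a relation out separates Possibly related from Unrelated only. It does nothing to separate it from Unlikely to be related.

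**2. Do the numbered criteria break the tie?**

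Both lists use the same four facts: (1) reasonable timing, (2) no ready alternative cause, (3) resolution or lessening when the product is stopped, (4) a known response pattern. Under Unlikely to be related, facts 1 and 4 are negated but 2 and 3 are not. Criterion 2 is word for word the same in both lists. Criterion 3 reads "disappears or is decreased upon removal of the IP", which I treat as the same fact as stopping the product.

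Let a be the number met of facts 1 and 4 (0 to 2), and b the number met of facts 2 and 3 (0 to 2).

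- Possibly related: a + b ≥ 2.
- Unlikely to be related, as written: (2 − a) + b ≥ 2, that is b ≥ a.

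| a | b | Patterns | Possibly | Unlikely |
|---|---|---|---|---|
| 0 | 0 | 1 | no | yes |
| 0 | 1 | 2 | no | yes |
| 0 | 2 | 1 | yes | yes |
| 1 | 0 | 2 | no | no |
| 1 | 1 | 4 | yes | yes |
| 1 | 2 | 2 | yes | yes |
| 2 | 0 | 1 | yes | no |
| 2 | 1 | 2 | yes | no |
| 2 | 2 | 1 | yes | yes |

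Totals over 2^4 = 16 patterns:

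- both: 1 + 4 + 2 + 1 = 8
- Possibly related only: 1 + 2 = 3
- Unlikely to be related only: 1 + 2 = 3
- neither: 2

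Three details follow.

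- An event meeting all four Possibly related criteria (a = 2, b = 2) also qualifies as Unlikely to be related.
- Of the 1 + 4 + 1 = 6 patterns with exactly two Possibly related criteria met, 5 also qualify as Unlikely to be related. The exception is timing plus known pattern alone.
- Of the 8 overlapping patterns, 2 + 1 = 3 meet at least three criteria, and so reach the threshold for Probably related as well.

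**3. What correcting the criteria alone would do**

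If criteria 2 and 3 of Unlikely to be related are negated, its rule becomes (2 − a) + (2 − b) ≥ 2, that is a + b ≤ 2. The overlap shrinks to a + b = 2, which is 6 of 16 patterns. Possibly related only is 2 + 2 + 1 = 5, Unlikely to be related only is 1 + 2 + 2 = 5, and no pattern is left uncovered. The exact ties still need a rule.

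**The case against.** The strongest reply is that the categories are defined. Each has an operational criteria rule, and SAP 15.1 says plainly which categories count. This stands to the extent that the definitions overlap and none is missing. A reader might infer that the boundary is undefined, or that a genuinely possible relation has no category at all. The text does not support that. An event meeting two of the four Possibly related criteria may be given that label whatever the opening sentence says, and the gap exists only among the opening sentences. The reply does not rescue the boundary, because the criteria overlap too.

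A second reply is that sending doubtful events to a counted category is a conservative convention. It could be, if the next category did not claim the same events.

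A third reply is that the impact is limited, and most of it stands. The safety endpoint is the incidence of all TEAEs, which does not use causality. All SAEs go to the sponsor within 24 hours whatever the attribution (protocol 9.4). Raters are masked, so in the masked period inconsistent labels should mainly add noise and should not favour an arm. The relationship summaries show the two categories separately, although the split they show is the unreliable part.

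A reader might also infer a route to unmasking, since protocol 7.8 lets the Medical Monitor unmask "If a drug-related serious adverse event" is reported. The visible text does not tie that term to the 9.3 categories. Its cross-reference there is to the SAE definition in 9.2, the power is discretionary, the counting rule in SAP 15.1 concerns TEAE tables, and part of 7.8 is blacked out. I draw no conclusion about unmasking.

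**Conclusion.** The concern holds as overlapping definitions. The opening sentences of Possibly related and Unlikely to be related express one judgement, the criteria fail to separate them in 8 of 16 patterns, and the SAP's treatment-related cut lies on that boundary. Table 14.3.7, Listing 16.2.7.2.3 and the relationship summaries are therefore rater-dependent.

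The 8 of 16 counts logical patterns. It is not a proportion of events, because the patterns are not equally likely in practice. It assumes that each criterion is answered yes or no, and that stopping and removing the product mean the same thing. The number of subjects affected cannot be estimated: the sample size is blacked out, and the documents give no frequency of doubtful events. Total TEAE incidence does not change. This is a modest fault in a descriptive safety output, worth correcting because the correction is cheap.

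**What to change.** Make one edit to protocol 9.3 with these parts:

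1. Reword the opening of Possibly related along these lines: *there is a reasonable possibility that the IP caused the AE, and another cause is also plausible*. Keep the judgement that a relation is unlikely for Unlikely to be related.
2. Negate criteria 2 and 3 of Unlikely to be related, so that all four criteria point away from a relation.
3. State which category applies when exactly two of the four criteria are met. Assigning these ties to Possibly related keeps it distinct from Probably related. If they went to Unlikely to be related, Possibly related would begin at three criteria, the threshold that Probably related already uses.
4. Copy the text into the CRF completion guideline and notify sites.

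The parts belong together. Rewording the sentence alone leaves the 8 overlapping patterns across the SAP cut, and correcting the criteria alone leaves the 6 ties and the shared description. After the full edit, the counting rule in SAP 15.1 can stand as written.

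The cost is a short protocol change, a guideline update and a site note, with no extra patients or data. The small downside is that causality calls made before the change may need a query.

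### Protocol 9.3: two of the four *Unlikely to be related* criteria still point towards relatedness, and no tie-break separates *Possibly* from *Unlikely*, where SAP 15.1 draws the treatment-related line

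*Protocol*

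**What the plan says.** Protocol 9.3 asks the Investigator to place each AE or SAE in one of five categories. *Probably*, *Possibly* and *Unlikely* each have a lead-in judgement followed by a checklist of four items: timing, alternative causes, course after the product is stopped, and known response pattern.

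- *Probably related*. Lead-in: the events "are felt with a high degree of certainty to be related to the IP". Threshold: "An adverse event may be considered probable if or when (must meet at least three of the four criteria".
- *Possibly related*. Lead-in, in paraphrase: a relationship is thought improbable but cannot be excluded. Threshold: two of the same four items. The last two, "3) disappears or is decreased upon discontinuation of the IP; or (4) it follows a known response pattern to treatment with IP", are both in the positive form.
- *Unlikely to be related*. Lead-in: the events "are judged likely to be unrelated to the IP". Threshold: "An adverse event may be considered unlikely if or when (must meet at least two of the four criteria". Items (1) and (4) are put in the negative. Item (2) still begins "it could not readily have been produced by", as in the two categories above it, and item (3) keeps its positive sense: "3) disappears or is decreased upon removal of the IP; or (4) it does not follow a known response pattern to treatment with IP".

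*Definitely* has its own three criteria, all required. *Unrelated* has no checklist; it is reserved for events that are certainly due to something else. Section 9.3 does not say what to do when an event meets more than one list.

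SAP 15.1 repeats the five labels and counts the top three as treatment-related. *Unlikely* and *Unrelated* are not counted.

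**The concern.** The absence of another ready cause and improvement off the product are both evidence for a drug effect, and 9.3 uses them that way under *Probably* and *Possibly*. Under *Unlikely* the same two findings count towards the opposite conclusion. Together they satisfy that checklist whatever the timing or response pattern.

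What is at stake is the boundary between *Possibly* and *Unlikely*, because SAP 15.1 defines treatment-related TEAEs there. An event filed as *Unlikely* by this route could drop out of Table 14.3.7, Listing 16.2.7.2.3 and the treatment-related line of the overall TEAE summary. It would still appear in the by-relationship summaries of SAP 15.1, but under the wrong category.

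**Working it through.** The documents give no figure to reproduce, so the check is an enumeration. Let T = plausible timing, N = no ready alternative cause, D = disappears or decreases off the product, K = known response pattern, each coded 1 (yes) or 0 (no). This gives 2^4 = 16 patterns. The small wording differences in item (3) between categories are taken as equivalent.

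From Protocol 9.3:
- *Probably*: T + N + D + K ≥ 3
- *Possibly*: T + N + D + K ≥ 2
- *Unlikely* as written: (1 − T) + N + D + (1 − K) ≥ 2
- *Unlikely* with (2) and (3) reversed: 4 − (T + N + D + K) ≥ 2

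| Signs present | Sum of signs | *Unlikely* score as written | *Unlikely* score, (2) and (3) reversed |
|---|---|---|---|
| none | 0 | 2 | 4 |
| T | 1 | 1 | 3 |
| N | 1 | 3 | 3 |
| D | 1 | 3 | 3 |
| K | 1 | 1 | 3 |
| TN | 2 | 2 | 2 |
| TD | 2 | 2 | 2 |
| TK | 2 | 0 | 2 |
| ND | 2 | 4 | 2 |
| NK | 2 | 2 | 2 |
| DK | 2 | 2 | 2 |
| TND | 3 | 3 | 1 |
| TNK | 3 | 1 | 1 |
| TDK | 3 | 1 | 1 |
| NDK | 3 | 3 | 1 |
| TNDK | 4 | 2 | 0 |

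**As written.** *Probably* is met by 5 patterns, of which 3 also meet *Unlikely* (TND, NDK, TNDK). *Possibly* is met by 11, of which 8 also meet *Unlikely* (those three plus TN, TD, ND, NK, DK). Four of the 8 (ND, TND, NDK, TNDK) have both un-reversed items present. ND scores 4 of 4 on *Unlikely*. T alone and K alone meet none of the three lists.

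**Reversing (2) and (3) only.** Overlap with *Probably* falls from 3 to 0, and no pattern is left without a list. Overlap with *Possibly* goes from 8 to 8 − 3 + 1 = 6 of 11: TND, NDK and TNDK leave and TK joins. Among the patterns with exactly two signs, overlap rises from 5 of 6 to 6 of 6. This is built in: two signs present means two absent, so both two-of-four lists are met.

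**Tie-break only.** If overlapping events go to the stronger category but the text of (2) and (3) stays, none of the 11 is lost to *Unlikely*, but T alone and K alone still meet no list.

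**Both changes.** *Probably* 5 + *Possibly* 6 + *Unlikely* 5 = 16, one of these three categories per pattern. This leaves out *Definitely* and *Unrelated*. If the differently worded second criterion of *Definitely* is read as equivalent to N, TNK and TNDK also meet *Definitely*, leaving 5 − 2 = 3 for which *Probably* is the strongest list met. That does not move the *Possibly*/*Unlikely* boundary.

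**The case against.** The strongest reply is that the checklists are aids and the lead-in sentences decide. All three lists are permissive, and an Investigator highly certain that an event is related cannot also judge it likely unrelated. For *Probably* against *Unlikely* this largely stands. A reader might infer from 3 of 5 that probably related events will be filed as unlikely; the text permits that but does not force it, and the lead-ins work against it.

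The reply fails for *Possibly*. Its lead-in and that of *Unlikely* both say, in nearly the same words, that a relationship is improbable. Judgement therefore has little to separate them, and the checklist has to do it. SAP 15.1 does refer to the strongest relationship, but as a way of tabulating TEAEs, not of assigning a category to an event.

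A second reply is that the missing reversals are blamed for too much. This stands: 5 of the 8 *Possibly* overlaps remain after reversal and one is added. A reader might take all 8 as the product of the two un-reversed items, but most of the overlap comes from the equal thresholds and the lack of a tie-break.

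A third reply is that a rule always imposing the strongest category met would turn judgement into a score, and could force *Possibly* on an event that is certainly extraneous. This also stands, and the tie-break below is limited accordingly.

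**Conclusion.** The *Unlikely to be related* checklist is wrong as written in two of its four items, and the *Possibly*/*Unlikely* boundary has no tie-break. On the checklists alone, 3 of 5 *Probably* and 8 of 11 *Possibly* patterns also meet *Unlikely*. The counts assume that every item can be answered yes or no and give each pattern equal weight. They are not misclassification rates, and the documents offer no basis for one.

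The effect is confined to outputs that use the assigned category. A reader might infer that the main safety results are at risk. They are not: the safety endpoint in Protocol section 3 and SAP 2.4 is TEAE incidence regardless of cause, and Protocol 9.4 requires all SAEs to be reported within 24 hours. A reader might also link this to the Medical Monitor's option to unmask for a drug-related SAE (Protocol 7.8, SAP 4.2), but the documents do not define that term by these categories.

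This is a wording correction worth making, not a threat to the trial's conclusions.

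**What to change.** All changes belong in Protocol 9.3; SAP 15.1 can stay as it is.

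1. Under *Unlikely to be related*, delete the word *not* from item (2), so that a ready alternative cause counts towards *Unlikely*. Change item (3) to: *it does not disappear or decrease upon removal of the IP*.
2. Add that an event meeting both the *Possibly* and the *Unlikely* checklists is assigned *Possibly*, unless the Investigator judges it *Unrelated* as 9.3 defines that category. This settles the six ties that reversal alone leaves.
3. Reword the *Possibly* lead-in so that it no longer describes the category below it.

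The tie-break has to act when the Investigator makes the assessment. Section 9.3 says "This causality assessment must be signed and dated by the person making the evaluation in source documents", but no visible text requires item-level answers to be recorded. The case report form is not among the documents, so one cannot assume that ties could be found later at analysis.

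The cost is a short amendment with whatever approvals Protocol 11.13 requires, a note to sites, and a check of events already assessed under the present wording. The treatment-related TEAE count may rise, by an amount that the documents do not allow to be estimated.
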